15.2	Data Management Procedures	26
15.3	Data Quality Control and Reporting.....	26
15.4	Archival of Data	26
15.5	Availability and Retention of Investigational Records.....	27
15.6	Monitoring	27
15.7	Subject Confidentiality	27
16	ADMINISTRATIVE, ETHICAL, REGULATORY CONSIDERATIONS	27
16.1	Protocol Amendments	27
16.2	Institutional Review Boards and Independent Ethics Committees.....	28
16.3	Informed Consent Form.....	28
16.4	Publications	29
16.5	References	29

LIST OF ABBREVIATIONS

AE	adverse event
ALT	alanine aminotransferase
AST	aspartate aminotransferase
BUN	blood urea nitrogen
CFR	Code of Federal Regulations
CRF	case report form
FDA	Food and Drug Administration
GCP	Good Clinical Practice
HIPAA	Health Insurance Portability and Accountability Act of 1996
ICF	informed consent form
ICH	International Conference on Harmonisation
IEC	Independent Ethics Committee
IRB	Institutional Review Board
IV	intravenous
PI	Principal Investigator
PK	pharmacokinetic
SAE	serious adverse experience
SGOT	serum glutamic oxaloacetic transaminase
SGPT	serum glutamate pyruvate transaminase

PROTOCOL SYNOPSIS

TITLE	Clearance of 25-hydroxyvitamin D in cystic fibrosis
SPONSOR	[name]
FUNDING ORGANIZATION	National Institute of Diabetes and Digestive and Kidney Diseases (P30DK089507, R01DK099199)
NUMBER OF SITES	Single-site study
RATIONALE	
Cystic fibrosis (CF) is among the most common autosomal recessive disorders and leads to serious, life threatening respiratory, infectious, and bone complications. Vitamin D deficiency is highly prevalent among CF patients, is unusually resistant to standard vitamin D supplementation regimens, and may contribute to osteoporosis and immune dysfunction. The prevalence of vitamin D deficiency, determined by circulating concentrations of 25-hydroxyvitamin D (25(OH)D), remains as high as 90% in CF patients despite modern practices of vitamin D supplementation and pancreatic enzyme replacement.
 
A number of plausible hypotheses may explain the marked vitamin D deficiency intrinsic to CF. Pancreatic insufficiency, the most common gastrointestinal CF complication, leads to malabsorption of fat soluble vitamins A, D, E, and K. Hepatobiliary disease may impair the uptake of vitamin D₂ and D₃ into the liver for conversion into 25(OH)D, or may interfere with enterohepatic recirculation to enhance loss of vitamin D metabolites. Small intestinal bacterial overgrowth may further obstruct the gastrointestinal absorption of vitamin D. Finally, urinary losses of vitamin D binding protein and albumin, the major carriers of vitamin D metabolites, may contribute to lower circulating concentrations of vitamin D metabolites.
 
Proposed mechanisms to explain vitamin D deficiency in CF lack empiric supportive data. In this study, we will determine specific vitamin D metabolic disturbances that are intrinsic to CF patients and to explore their biologic sequelae. Identifying the causes of vitamin D deficiency in CF could suggest alternative treatments, such as intramuscular vitamin D preparations, activated vitamin D agents, or higher doses of supplements, to improve clinical outcomes that have been linked with vitamin D deficiency, such as bone disease and infection.

STUDY DESIGN	This is a single-dose, open-label pharmacokinetic study that uses intravenous administration of a stable deuterium-labeled 25(OH)D ₃ to evaluate the metabolic clearance of 25(OH)D ₃ .

	Allocation: Non-Randomized Intervention Model: Single Group Assignment Masking: Open Label
PRIMARY OBJECTIVE	
The goal of this study is to define 25(OH)D₃ catabolism in CF patients using gold standard pharmacokinetics studies. Specifically, we will evaluate the metabolic clearance of 25(OH)D₃ among participants with CF and matched control subjects. The goal of this work is to provide the first comprehensive characterization of vitamin D metabolism in CF patients and promote novel hypotheses for subsequent studies.

SECONDARY OBJECTIVES	
 • To explore the biochemical pathways through which 1,25(OH)D₃ is metabolized, and the effects of CKD and race on these pathways, by evaluating the appearance and disappearance of labeled metabolites of 25(OH)D₃. • To determine clinical and biochemical factors that are correlated with the metabolic clearance of 25(OH)D₃. • To evaluate biomarkers of 25(OH)D₃ clearance. • To compare monocyte expression of vitamin D-related genes in CF patients versus healthy controls
NUMBER OF SUBJECTS	Up to 20
SUBJECT SELECTION CRITERIA	
Inclusion Criteria:
 
 • Age \geq 18 years • Serum total 25(OH)D 10-50 ng/mL 
Exclusion Criteria:
 
 • Primary hyperparathyroidism • Gastric bypass • Tuberculosis or sarcoidosis • Current pregnancy • Use of vitamin D₃ or vitamin D₂ supplements exceeding a mean daily dose of 400 IU within 3 months (wash-out allowed) • Use of 1,25(OH)₂D₃ or an analogue, calcimimetics, or medications known to induce CYP24A1 within 3 months (wash-out allowed) • Serum calcium $>$ 10.1 mg/dL • Hemoglobin $<$ 10 g/dL
TEST PRODUCT, DOSE, AND ROUTE OF ADMINISTRATION	We will administer deuterated 25(OH)D ₃ -d6 [26,26,26,27,27,27-d6] intravenously. The labeled 25(OH)D ₃ will be prepared in a co-solvent formulation of ethanol (10%) and propylene glycol (40%). To ensure reliable detection of circulating deuterated 25(OH)D ₃ , without administering a dose that might alter the underlying vitamin D metabolism, we aim to

	administer a dose that results in a peak deuterated 25(OH)D ₃ concentration of approximately 5 ng/mL. The administered dose will be calculated as the targeted peak serum deuterated 25(OH)D ₃ (5 ng/mL) multiplied by blood volume.
CONTROL PRODUCT, DOSE AND ROUTE OF ADMINISTRATION	There is no control product.
DURATION OF SUBJECT PARTICIPATION AND DURATION OF STUDY	Subjects will be on study for approximately 12 weeks Screening: approximately 4 weeks Treatment: 1 day (subjects to the University of Washington Clinical Research Center) Follow-up: 8 weeks The total duration of the study is expected to be up to 3 years for subject recruitment and an additional 12 weeks for final subject follow-up.
CONCOMITANT MEDICATIONS	Allowed: 
Vitamin D supplements (cholecalciferol, ergocalciferol) not to exceed a mean daily dose of 400 IU Prohibited (within last 3 months, wash-out allowed): 
1,25(OH)₂D₃ or an analogue (e.g. paricalcitol, hectorol)Calcimimetics (e.g. cinacalcet)Medications known to potently induce or inhibit CYP24A1 or CYP3A4
EFFICACY EVALUATIONS	None
PRIMARY ENDPOINT	
Metabolic clearance of labeled 25(OH)D₃ (administered dose/AUC)
SECONDARY ENDPOINTS	
AUC of labeled 25(OH)D₃Terminal half-life of labeled 25(OH)D₃Volume of distribution in the central compartment of labeled 25(OH)D₃Monocyte transcription of CYP27B1, CYP24A1, VDR, and cathelicidin
OTHER EVALUATIONS	Metabolic formation clearance (metabolite/parent AUC ratio) for metabolites of labeled 25(OH)D ₃
SAFETY EVALUATIONS	Change in the serum concentrations of calcium, creatinine, AST, and ALT and from baseline to 7 days after 25(OH)D ₃ administration Incidence of adverse events

PLANNED INTERIM ANALYSES	This is not a clinical trial with an efficacy outcome, and it is neither randomized nor blinded. For interim analyses are not planned.
STATISTICS Primary Analysis Plan	We will examine the distribution of 25(OH)D ₃ clearance by CF status using box plots and summary statistics. We will test associations of CF status with 25(OH)D ₃ clearance (continuous outcome variable) using linear regression. Models will be adjusted for age, gender, body size, baseline 25(OH)D concentration, and other covariates strongly related to 25(OH)D ₃ clearance.
Rationale for Number of Subjects	For this descriptive study, our sample size of 20 was based on feasibility and funding considerations.

1 BACKGROUND

Cystic fibrosis (CF) is among the most common autosomal recessive disorders and leads to serious, life threatening respiratory, infectious, and bone complications. Vitamin D deficiency is highly prevalent among CF patients, is unusually resistant to standard vitamin D supplementation regimens, and may contribute to osteoporosis and immune dysfunction. The prevalence of vitamin D deficiency, determined by circulating concentrations of 25-hydroxyvitamin D (25(OH)D), remains as high as 90% in CF patients despite modern practices of vitamin D supplementation and pancreatic enzyme replacement. A number of plausible hypotheses may explain the marked vitamin D deficiency intrinsic to CF. Pancreatic insufficiency, the most common gastrointestinal CF complication, leads to malabsorption of fat soluble vitamins A, D, E, and K. Hepatobiliary disease may impair the uptake of vitamin D₂ and D₃ into the liver for conversion into 25(OH)D, or may interfere with enterohepatic recirculation to enhance loss of vitamin D metabolites. Small intestinal bacterial overgrowth may further obstruct the gastrointestinal absorption of vitamin D. Finally, urinary losses of vitamin D binding protein and albumin, the major carriers of vitamin D metabolites, may contribute to lower circulating concentrations of vitamin D metabolites. Proposed mechanisms to explain vitamin D deficiency in CF lack empiric supportive data. In this study, we will determine specific vitamin D metabolic disturbances that are intrinsic to CF patients and to explore their biologic sequelae. Identifying the causes of vitamin D deficiency in CF could suggest alternative treatments, such as intramuscular vitamin D preparations, activated vitamin D agents, or higher doses of supplements, to improve clinical outcomes that have been linked with vitamin D deficiency, such as bone disease and infection.

1.1 Overview of Clinical Studies

Intravenous deuterated 25(OH)D₃ has been used previously in humans in one published study, and intravenous tritiated 25(OH)D₃ has been used in humans in several previous studies.¹⁻⁵ In addition deuterium is used extensively in the study of metabolism and is considered safe.⁶

2 STUDY RATIONALE

Vitamin D deficiency is overwhelmingly prevalent in cystic fibrosis. Vitamin D deficiency is the most common and persistent nutritional inadequacy in CF.⁷ Vitamin D is normally generated in the skin as vitamin D₃ (cholecalciferol) or consumed in the diet as either vitamin D₃ or vitamin D₂ (ergocalciferol).⁸ Vitamin D₃ and vitamin D₂ are next converted in the liver to 25-hydroxyvitamin D₃ (25(OH)D₃) and 25-hydroxyvitamin D₂ (25(OH)D₂), respectively, which together are referred to as total 25-hydroxyvitamin D (25(OH)D). Circulating 25(OH)D concentrations are the accepted clinical markers of vitamin D status and are markedly reduced in CF patients. The prevalence of vitamin D deficiency in CF is as high as 90%, depending on the patient population and 25(OH)D threshold used to define deficiency (20-30 ng/mL).⁹⁻¹² Given the role of vitamin D in calcium homeostasis and bone health, the measurement and treatment of vitamin D deficiency is an integral component of clinical CF care. However, CF patients inadequately respond to vitamin D supplementation, such that 25(OH)D concentrations remain insufficient in many CF patients despite treatment.¹²⁻¹⁴

The cause of vitamin D deficiency in cystic fibrosis is unclear. Malabsorption of fat soluble vitamins, including vitamin D, is likely a major contributor to vitamin D deficiency in CF.^{15,16}

Pancreatic insufficiency is the most plausible mechanism of fat malabsorption; the chloride channel cystic fibrosis transmembrane conductance regulator (CFTR), which is present in enterocytes, does not appear to directly contribute to malabsorption. CF patients have variable and often poor plasma 25(OH)D responses to dietary vitamin D supplementation, which could be due in part to reduced bioavailability.¹²⁻¹⁶ However, in studies administering parenteral vitamin D₂ and ultraviolet light (one study each), plasma 25(OH)D response was also markedly impaired.^{7,17} In addition, higher than usual antibiotic doses are often required in CF patients, suggesting induction of metabolizing enzymes that may overlap with those which metabolize vitamin D.¹⁸⁻²¹ Together, these findings suggest additional defects in vitamin D metabolism in CF patients. For full hormonal activity, 25(OH)D must be converted to the active vitamin D hormone, 1,25-dihydroxyvitamin D (1,25(OH)₂D). In addition, 25(OH)D can undergo a series of catabolic steps leading to its elimination (**Figure 1**).²² The most common route of 25(OH)D₃ catabolism begins with conversion to 24,25-dihydroxyvitamin D₃ by the cytochrome P450 enzyme CYP24A1. Drs. [name] and [name] (Co-investigators) have discovered that 25(OH)D₃ also undergoes hydroxylation at the 4-position and sulfation at the 3-O-position. The resulting metabolites, 4 β ,25(OH)₂D₃ and 25(OH)D₃-3-sulfate, respectively, are generated in enterocytes and hepatocytes by CYP3A4 and SULT2A1.^{23,24} Vitamin D metabolic enzymes are regulated by parathyroid hormone (PTH) and fibroblast growth factor-23 (FGF-23) as well as 1,25(OH)₂D itself. Our group has contributed to an expanding knowledge of dysregulated vitamin D metabolism in chronic kidney disease, in which both vitamin D activation and catabolism are impaired.^{22,25} However, little is known about the vitamin D metabolic axis in CF in terms of vitamin D activation, vitamin D catabolism, or the hormonal response to vitamin D deficiency. Clearance of 25(OH)D may be affected in CF by altered enterohepatic function of CYP3A4 and SULT2A1. In addition, enterohepatic vitamin D circulation, in which sulfated 25-hydroxyvitamin D is secreted in bile and delivered to target enterocytes, may be disrupted, leading to loss of conjugated vitamin D in the stool and altered enteric metabolism. Small bowel bacterial overgrowth due to impaired gastrointestinal mobility may further reduce absorption of vitamin D. Finally, vitamin D binding protein (DBP) and albumin, which carry circulating vitamin D metabolites, may be lost in the urine.²⁶ Defining which of these potential metabolic defects is clinically relevant may lead to improved methods of vitamin D deficiency diagnosis and treatment.

Impaired vitamin D metabolism may have broad adverse health effects in cystic fibrosis. 1,25(OH)₂D₃ binds to the intracellular vitamin D receptor to modulate transcription of genes involved in bone health, inflammation, and blood pressure. Vitamin D is a central determinant of calcium and phosphate absorption from gastrointestinal tract to provide mineral content for growing bones.²⁷ Moreover, vitamin D deficiency may directly impair muscle strength, thereby

[figure not shown]

Figure 1. 25(OH)D₃ metabolism.

indirectly reducing bone density. Monocytes metabolize vitamin D and require 1,25(OH)₂D₃ for robust immune function. For example, within monocytes, autocrine metabolism of 25(OH)D₃ to 1,25(OH)₂D₃ by CYP27B1 is required for the expression of cathelicidin and resulting activity against *mycobacterium tuberculosis*.^{28,29} Addition of 1,25(OH)₂D₃ to cultured monocytes reduces expression of pro-inflammatory cytokines IL-1, IL-6, IL-8, and TNF- α , and promotes generation of regulatory Th2 lymphocytes. Disruption of the vitamin D receptor directly stimulates the renin-angiotensin-aldosterone system, promoting hypertension and arteriosclerosis. In large population studies, vitamin D deficiency, defined by lower circulating 25(OH)D concentrations, is associated with cardiovascular disease events, fractures, and cancer. The clinical consequences of vitamin D deficiency in CF patients are not yet clearly defined; however, bone disease and infections represent major clinical complications of CF that are plausibly influenced by vitamin D deficiency. A more detailed understanding of the relationships between vitamin D metabolism and bone disease and infections in CF may provide new opportunities to reduce these important clinical complications.

Multiple vitamin D interventions are widely available, but their proper use in CF awaits identification of specific vitamin D metabolic disturbances. Supplementation with vitamin D₃ or D₂ may be improved by administration of higher oral dosage programs or intramuscular injections. Ultraviolet light exposure has been used in small studies of CF patients and may augment concurrent vitamin D supplementation. If identified, cytochrome P-450 enzymes with altered activities in CF could be targeted for intervention. Finally, vitamin D receptor agonists (1,25(OH)₂D and its analogues) are widely used in patients with kidney disease and could play a role in the treatment of vitamin D deficiency in CF.

2.1 Risk / Benefit Assessment

This study will not provide any direct benefit to the study subjects. Individual subjects may have a modestly reduced chance of adverse health events because their care will be monitored more closely than it might otherwise. Future patients may benefit from these studies by virtue of knowledge gained about the pathophysiology and ascertainment of impaired vitamin D metabolism.

The risks of administering deuterated 25(OH)D₃ in tracer quantities are low. 25(OH)D₃ is a naturally occurring substance and generally circulates in concentrations of 10-50 ng/mL. The deuterated 25(OH)D₃ we propose to administer differs from the naturally occurring form only by the substitution of 6 hydrogen atoms with deuterium. This isotope is stable and has metabolic and biologic characteristics identical to the naturally occurring form. We will administer quantities intended to make small changes in total circulating 25(OH)D₃ concentration, i.e., an increase of 5 ng/mL.

There is some risk of hypercalcemia with the administration 25(OH)D₃, but this risk is minimized by excluding participants with baseline 25(OH)D > 50 ng/mL and by administering quantities that raise 25(OH)D by only approximately 5 ng/mL. We will monitor for hypercalcemia during our research. If instances of hypercalcemia are observed, we will change our study protocol accordingly to prevent hypercalcemia in future participants. This study also includes placement of peripheral intravenous catheters and blood draws. Risks include discomfort and minor bleeding associated with catheter placements and anemia due to blood sampling.

3 STUDY OBJECTIVES

3.1 Primary Objective

The goal of this study is to define 25(OH)D₃ catabolism in CF patients using gold standard pharmacokinetics studies. Specifically, we will evaluate the metabolic clearance of 25(OH)D₃ among participants with CF and matched control subjects. The goal of this work is to provide the first comprehensive characterization of vitamin D metabolism in CF patients and promote novel hypotheses for subsequent studies.

3.2 Secondary Objectives

- To explore the biochemical pathways through which 25(OH)D₃ is metabolized, and the effects of CF on these pathways, by evaluating the appearance and disappearance of labeled metabolites of 25(OH)D₃.
- To determine clinical and biochemical factors that are correlated with the metabolic clearance of 25(OH)D₃.
- To evaluate potential biomarkers of 25(OH)D₃
- To compare monocyte expression of vitamin D-related genes in CF patients *versus* healthy controls

4 STUDY DESIGN

This is a cross-sectional, observational study that uses the intravenous administration of stable isotope-labeled 25(OH)D₃ to evaluate the metabolic clearance of 25(OH)D₃. It is a single-dose, open-label PK study of 25(OH)D₃.

We will recruit a total of up to 20 study subjects: 10 with and 10 without CF. Subjects who provide written informed consent and qualify at screening will receive a single dose of intravenous labeled 25(OH)D₃. Subsequent blood draws and urine collections will be used to determine the metabolic clearance of 25(OH)D₃ and related parameters.

5 CRITERIA FOR EVALUATION

5.1 Primary Efficacy Endpoint

The primary outcome of interest is the metabolic clearance of labeled 25(OH)D₃.

We will measure serum concentrations of 24,25(OH)₂D₃, 25(OH)D₃, 25(OH)D₂, 1,25(OH)₂D₃ and 1,25(OH)₂D₂ at the University of Washington by mass spectrometry. For each participant and time point, a single serum aliquot is used to measure this panel of vitamin D metabolites using by immunoaffinity extraction and HPLC-mass spectrometry (Xevo TQ, Waters Corp., Milford, MA) with deuterated internal standards.^{25,30-32}

For each subject, non-compartmental analysis of plasma concentration versus time data will be performed using Phoenix software (Pharsight, Cary, NC). Clearance will be calculated as administered 25(OH)D₃ dose divided by 25(OH)D₃ AUC. We focus on clearance as our primary outcome because it reflects the metabolism of 25(OH)D₃ accounting for circulating 25(OH)D₃ concentration (units of volume/time, akin to creatinine clearance). Clearance is independent of volume of distribution, in contrast to $t_{1/2}$, which will be evaluated as a secondary outcome. Clearance will be evaluated with and without adjustment for body size.

5.2 Secondary Efficacy Endpoints

- AUC of labeled 25(OH)D₃
- Terminal half-life of labeled 25(OH)D₃
- Volume of distribution in the central compartment of labeled 25(OH)D₃
- Metabolic formation clearance (metabolite/parent AUC ratio) for metabolites of labeled 25(OH)D₃
- Monocyte transcription of CYP27B1, CYP24A1, VDR, and cathelicidin

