8.4.1 Dosage/Dosage Regimen

Each participant will receive a single intravenous dose of deuterated 25(OH)D₃. We will use body size-based dosing to target a peak achieved deuterated 25(OH)D₃ concentration of 5 ng/mL. The target of 5 ng/mL was selected because it will allow precise tracking of circulating deuterated 25(OH)D₃ concentration throughout follow-up (based on known limits of detection for our assay) without substantially perturbing underlying vitamin D status. Theoretically, the dose required to achieve a 5 ng/mL increment in deuterated 25(OH)D₃ concentration can be calculated as the targeted peak concentration multiplied by the volume of distribution, which for 25(OH)D₃ is expected to be equal to blood volume. We will use the formula of Nadler et al (1962) to estimate blood volume for each participant. We will begin the study by administering to each participant a dose of 5 ng/mL x estimated blood volume. A typical dose will be 25-30 mcg. We will monitor achieved 25(OH)D₃ concentrations real time. If our initial approach fails to achieve peak 25(OH)D₃ concentrations near 5 ng/mL, we will revise our approach for future participants, as indicated. For example, if mean peak achieved 25(OH)D₃ concentrations are near 2.5 ng/mL with our initial approach, we will increase our dose by a factor of two. We will not exceed a dose of 100 mcg for any participant.

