14.3 Analysis of Primary Endpoint

We will examine the distribution of 25(OH)D₃ clearance by CF status using box plots and summary statistics. We will explore the distribution of 25(OH)D₃ clearance by key covariates (age, gender, and baseline concentrations of 25(OH)D, PTH, FGF-23, and vitamin D binding protein) using locally weighted scatterplot smoothing (LOWESS), cubic splines, and box plots. We will pay particular attention to the associations of PTH and FGF-23 with 25(OH)D₃ clearance, including multivariable modeling to determine independent associations. We will test associations of CF status with 25(OH)D₃ clearance (continuous outcome variable) using linear regression. Models will be adjusted for age, gender, body size, baseline 25(OH)D concentration, and other covariates strongly related to 25(OH)D₃ clearance.

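### If the dosing formula is revised mid-study, raw AUC by CF status is a blurred or biased comparison; any such comparison should use AUC per administered dose

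*Combined protocol and SAP*

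**What the plan says.** The Synopsis and Section 5.2 list "AUC of labeled 25(OH)D₃" among the secondary endpoints. Neither defines it per unit of dose. Section 14.4 has secondary endpoints analysed as the primary is, which under Section 14.3 means box plots, summaries and a linear regression on CF status. On covariates, Section 14.3 says: "Models will be adjusted for age, gender, body size, baseline 25(OH)D concentration, and other covariates strongly related to 25(OH)D₃ clearance".

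Section 5.1 ties AUC to dose: "Clearance will be calculated as administered 25(OH)D₃ dose divided by 25(OH)D₃ AUC".

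Section 8.4.1 starts each dose at the target peak multiplied by estimated blood volume, and adds: "A typical dose will be 25-30 mcg". It continues: "We will monitor achieved 25(OH)D₃ concentrations real time". If peaks miss the target, "we will revise our approach for future participants, as indicated". Its example is mean peaks at half the target, in which case "we will increase our dose by a factor of two". The ceiling is stated as "We will not exceed a dose of 100 mcg for any participant".

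Section 14.6 calls the study descriptive and gives no power calculation. No significance level is stated, nor the order in which CF patients and controls are enrolled.

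**The concern.** Take two participants of the same size with the same clearance, one dosed before a doubling and one after. Their clearances agree, but their AUCs differ twofold. A regression of AUC on CF status without dose treats that gap as noise if it falls within groups, and as a CF effect if it falls between them.

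Body-size adjustment does not remove this. Under one fixed formula, dose depends on estimated blood volume, so body-size terms absorb most of the dose variation. After a revision, people of the same size receive different doses.

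The open covariate clause does not clearly help either. Read literally, it selects variables strongly related to clearance. Under linear kinetics and at a given body size, dose is not such a variable. Only a looser reading, covariates related to whichever outcome is being analysed, would bring dose in.

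At stake is a secondary result that seems to contradict the clearance result, or hides a real difference, for a reason unrelated to metabolism.

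**Working it through.** **Inputs from the protocol.** 10 CF and 10 controls (Section 4); starting dose 5 ng/mL x blood volume, typical dose 25-30 mcg, example revision x2, ceiling 100 mcg (Section 8.4.1); clearance = dose/AUC (Section 5.1); named covariates (Section 14.3).

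**Assumptions.** Clearance CV 20-40%, log-normal; two-sided 5% level; linear kinetics; blood volume about 5.5 L; and all splits. Below, *a v b* is the number out of 10 in each group dosed under the revised formula.

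**Step 1: the protocol's own figures.** 5 ng/mL x 5 to 6 L = 25 to 30 mcg, which matches the typical dose (the volumes are back-calculated). Doubling gives 50-60 mcg. The ceiling would allow 100/30 = 3.3 to 100/25 = 4.0 times a typical dose. The sample size of 20 has no statistical inputs to reproduce.

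**Step 2: bias at equal clearance.** AUC = dose/clearance, so after a doubling the ratio of mean AUCs is (10 + a)/(10 + b): 18/19 = 0.95 at 8v9, 17/20 = 0.85 at 7v10, 15/20 = 0.75 at 5v10, 18/12 = 1.50 at 8v2, and 15/15 = 1.00 at 5v5.

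**Step 3: lost precision.** With share p of each group doubled, the variance of log AUC rises by p(1 - p)(ln 2)². At p = 0.5 this is 0.25 x 0.480 = 0.120. The log variance of clearance, ln(1 + CV²), is 0.039, 0.086 and 0.148 at CV 20, 30 and 40%. Total variance is therefore 4.1, 2.4 and 1.8 times as large.

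**Step 4: simulation of the planned model.** Outcome on CF, age, gender, blood volume and baseline 25(OH)D (14 residual degrees of freedom), 20,000 runs per cell, doubling, no true CF difference.

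| Split | AUC ratio | Raw AUC rejects (%), CV 20/30/40% |
|---|---|---|
| No revision | 1.00 | 4.7 / 4.9 / 4.9 |
| 8v9 | 0.95 | 2.0 / 3.1 / 3.4 |
| 7v9 | 0.89 | 4.6 / 5.2 / 4.9 |
| 7v10 | 0.85 | 16.4 / 12.3 / 9.5 |
| 5v10 | 0.75 | 46.4 / 30.7 / 22.2 |
| 5v5 | 1.00 | 0.2 / 0.8 / 1.3 |
| 7v3 | 1.31 | 16.7 / 14.1 / 12.3 |
| 8v2 | 1.50 | 64.8 / 45.6 / 33.1 |

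AUC/dose rejects in 4.4-5.4% of runs in every cell. Rates below 5% are no reassurance: the dose gap inflates the estimated standard error. Relative to AUC/dose, the raw-AUC standard error is 1.45/1.23/1.14 times as large at 8v9 and 2.08/1.59/1.38 times at 5v5. A two-sample t-test on log AUC shows the same pattern (3v7: 15-19%; 2v8: 43-81%).

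**Step 5: detection.** For an assumed true clearance 1.4 times higher in CF, CV 20/30/40%:

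- AUC/dose: 90/58/37%.
- Raw AUC, 9 CF and 8 controls doubled: 43/27/19%.
- Raw AUC, 8 CF and 9 controls doubled: 80/54/37%; here the bias happens to favour the true difference.
- Raw AUC, 5v5: 24/19/15%.

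**Step 6: size of the revision.** A 1.25-fold change raises the standard error only 1.02-1.17 times and gives 3-9% rejection, or 8-15% at 5v10. A 1.5-fold change gives 7-12% at 7v10 and 13-29% at 5v10.

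**Step 7: dose or version as a covariate.** The standard error grows by about 1/√(1 - r²), where r is the correlation of formula version with CF status. At 7v10, r = 0.42 gives 1.10; at 5v10, r = 0.58 gives 1.22; at 8v2, r = 0.60 gives 1.25. Simulated values for log dose are about 1.1, and 1.25-1.3 for the last two. At 0v10, r = 1: version cannot be separated from CF status, and the log-dose standard error is about 45 times that of AUC/dose. In that split raw AUC loses little or no precision (standard error ratio 1.00 on the log scale, 1.06-1.08 on the raw scale), so the error is pure bias.

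**The case against.** The strongest reply is that the primary endpoint already answers the question. Clearance is dose-normalised, and half-life, volume and the metabolite/parent AUC ratio do not scale with dose under linear kinetics. A misleading raw AUC would sit beside a sound result from the same data. This stands, and it is why the point ranks low.

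The problem is also conditional. It needs a revision that may never occur, a sizeable multiplier and, for bias, an uneven split. Concentrations are watched in real time and a sample is taken 5 minutes after dosing (Section 9.3), so a missed peak could be seen after few participants. That favours an early revision, where the cost is mainly precision and detection. This stands too. Still, the protocol itself foresees a revision, so the analysis should say how it will be handled.

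The third reply is that the open covariate clause could admit dose. On a looser reading it could, but the text does not settle this, and Step 7 shows that a covariate is not a safe remedy in every split.

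A reader might infer that dose revision undermines the CF comparison as a whole, that false positives will be inflated, or that precision is always lost. The documents support none of these. The primary endpoint is untouched, the split cannot be predicted because enrolment order is not stated, and a revision that coincides with group costs little or no precision.

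**Conclusion.** The point holds in conditional form and is confined to one secondary endpoint. If the formula is revised, the planned raw-AUC comparison loses precision when the revision falls within groups and is biased when the revised share differs by group. If revision and group coincide, it is essentially pure bias.

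For a doubling, the consequence runs from mainly lost precision and detection (early, mixed) to false-positive rates of 22-46% at 5v10 and 33-65% at 8v2. The larger figures need a later revision together with marked imbalance. A revision of about 1.25-fold matters little unless the mix is markedly uneven. With no revision, the body-size-adjusted comparison is essentially sound.

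The link between AUC and dose, the provision for revision and the missing dose term come from the protocol. The splits, CVs, true ratio and 5% level are assumptions. The study is descriptive, and any discrepancy could be traced by looking at clearance. Severity is the lowest grade: worth considering.

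**What to change.** - **Section 14.4:** state that any comparison of AUC by CF status will use AUC divided by administered dose.
- **Synopsis and Section 5.2:** present raw AUC descriptively, with administered dose and formula version tabulated by group.

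Log dose or formula version should not be offered as an equal alternative. Either costs precision in an uneven mix and fails if the revision coincides with group.

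The cost is a short wording change in three places and no new data, since administered dose is already needed to compute clearance. The drawback is that AUC/dose is the reciprocal of clearance. It restates the primary result, and the report should say that it is not independent evidence. No change to dosing is proposed.
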